3.3. Other Endpoints

3.3.1. Non-steroidal Anti-Inflammatory Drug (NSAID) Usage

Any NSAIDs taken as background medications during the study will be identified along with start and stop dates, average daily dose (mg) and treatment frequency (days per week). Details regarding the calculation can be found in [Appendix 1.1](#). This intake score will be calculated for each study period.

3.4. Baseline Variables

Period 1 baseline values will be defined as the last available value of the screening and baseline visits (eg, if the baseline visit value is missing and screening is available, the screening value will be used as baseline). Period 2 baseline is defined as the last value before treatment withdrawal. Period 3 baseline is defined as the last period 2 value before re-treatment starts. P-values for change from baseline will be calculated using the paired t-test.

For response endpoints defined using change from baseline (eg, ASAS40) period 1 baseline will always be used as the reference point.

3.5. Safety Endpoints

3.5.1. Adverse Events

Adverse events (AEs) recorded throughout the study will be coded using the MedDRA dictionary. The number and percentage of patients experiencing at least one adverse event will be summarized overall, and by body system and preferred term. In any given category, subjects will only be counted once. Adverse events will further be categorized and summarized by severity and study drug relationship, as well as those that cause withdrawal, result in a dose reduction or in concomitant therapy. Adverse events that occur up to 28- days after the last dose test article administration will be attributed to the treatment period.

3.5.2. Laboratory Evaluations

Laboratory evaluations include blood chemistry and hematology, urinalysis. Plasma and whole blood biobank may also be collected. Baseline for laboratory evaluations will be obtained from the baseline visit.

3.5.3. Vital Signs

Vital signs will include sitting systolic and diastolic blood pressure, sitting pulse, weight and height. Baseline for vital sign parameters will be obtained from the baseline visit.

3.5.4. Inflammatory Bowel Disease (IBD), Psoriasis, and Acute Anterior Uveitis

3.5.4.1. Inflammatory Bowel Disease

The proportion of subjects diagnosed with IBD during each period will be determined for each treatment group. The denominator will include only those subjects who did not have a history of IBD.

The proportion of subjects who had a flare of IBD during each period will also be calculated by treatment group. The denominator will include only those subjects with a previous history of IBD.

3.5.4.2. Psoriasis

The proportion of subjects with psoriasis or with a flare of psoriasis will be calculated in a manner similar to that described for IBD in the previous section. That is, there will be separate calculations done depending on whether or not subjects had psoriasis reported as part of their medical history.

In subjects who had a flare, the proportion of subjects who had change in psoriasis morphology will also be determined.

3.5.4.3. Acute Anterior Uveitis

The proportion of subjects with acute anterior uveitis or with a flare of such will be calculated in a manner similar to that described for IBD and psoriasis. That is, there will be separate calculations done depending on whether or not subjects had uveitis reported as part of their medical history.

In addition, for those subjects newly diagnosed and for those subjects who had a flare, the proportion of subjects who received treatment and the proportion of subjects who received certain types of treatment will also be summarized. For those subjects who had a flare, the mean number of flares will be calculated.

3.5.5. Nonstudy Medications

Prior and concomitant medications will be coded using the WHO Drug dictionary. The numbers of subjects using concomitant medications will be categorized by drug category and preferred term, and presented for each treatment group.

Nonstudy medications will be summarized separately for each period.

4. ANALYSIS SETS

4.1. Full Analysis Set

4.1.1. Period 1

The full analysis set for period 1 will include all subjects who took study medication and had one evaluation after baseline.

4.1.2. Period 2

The full analysis set for period 2 will include all subjects who had at least one evaluation during period 2.

4.1.3. Period 3

The full analysis set for period 3 will include all subjects who took study retreatment medication and had at least one evaluation after restarting active therapy.

4.2. 'Per Protocol' Analysis Set

A per-protocol population may be defined for sensitivity analysis of the primary and key secondary efficacy endpoints (ASDAS inactive disease, ASAS 40). This will be defined separately for the withdrawal and retreatment periods. The per-protocol populations will be defined as subsets of each FAS population excluding subjects who have a protocol violation that is thought to potentially affect efficacy, with focus on potential violations of inclusion criteria in each period. There will be no per protocol population defined for period 1 of the study.

4.3. Safety Analysis Set

The safety analysis set for each period will include all subjects who entered the period; for periods 1 and 3, subjects must also take one dose of investigational drug.

4.4. Other Analysis Sets

N.A.

5. GENERAL METHODOLOGY AND CONVENTIONS

The final primary analysis will be performed when all subjects have completed the study using the final study database.

5.1. Hypotheses and Decision Rules

This study is an open-label study with one treatment group. Inferences will be based on point estimates and confidence intervals, rather than on hypothesis tests.

Except where stated, all confidence intervals will be 2-sided 95% confidence intervals.

5.2. General Methods

This is an open-label study so the statistical focus will be on estimation rather than hypothesis testing. Efficacy and outcomes endpoint analyses will use the full analysis set (FAS), safety analyses will use the safety analysis set.

As a general guideline, the format of tables produced will follow the specifications outlined in this analysis plan. Descriptive statistics for categorical variables (nominal or ordinal) will include the number (frequency), and percentage of subjects at each level of response. Continuous variables will be summarized by sample size, mean, mean changes, standard deviation, 95% CIs, minimum, maximum, median and 25th and 75th percentile values.

5.2.1. Analyses for Binary Data

Dichotomous clinical and subject rated endpoints measured during Periods 1, 2 and 3 will be summarized as number evaluated, percent with response of interest and 95% confidence intervals. For response endpoints defined using change from baseline (eg, ASAS40) period 1 baseline will always be used as the reference point.

5.2.2. Analyses for Continuous Data

For continuous clinical and subject rated endpoints measured during Periods 1, 2 and 3, both raw and change values will be summarized with the following descriptive statistics: n, mean, standard deviation, min and max, median and the 25th and 75th percentiles (quartiles).

Summaries will be produced by visit. For periods 2 and 3 changes from both the original (period 1) baseline and the specific period baseline will be produced. Both observed cases (time point completers) and last observation carried forward LOCF summaries will be produced. For the LOCF summaries, no baseline values will be carried forward. Period 1 baseline values will be defined as the last available value of the screening and baseline visits (eg, if the baseline visit value is missing and screening is available, the screening value will be used as baseline). Period 2 baseline is defined as the last value before treatment withdrawal. Period 3 baseline is defined as the last period 2 value before re-treatment starts. P-values for change from baseline will be calculated using the paired t-test.

5.2.3. Analyses for Categorical Data

N.A.

5.2.4. Analyses for Time to Event Data

Kaplan-Meier (KM) estimates, including plots, will be used to illustrate the time course of flare after treatment withdrawal. In addition to summarizing the data from the current study, the KM plots will show subjects from protocol B1801031 who met the entry requirements for the current trial withdrawal period. Those subjects did not have treatment withdrawn and will serve as a reference for evaluating the impact of treatment withdrawal. As a sensitivity analysis a life table approach will be used to compare the time to flare between the 2 studies, with time intervals based on visit windows.

In addition to the KM summaries, Cox proportional hazards models will be used to estimate the hazard ratio of continuing (B1801031) to withdrawn (B1801381) subjects.

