Little is known about the effects of ETN withdrawal in subjects who have achieved a significant clinical response. A small study with a mixture of AS and nr-ax SpA patients having achieved a significant clinical response showed that approximately 75-80% of subjects had relapses after 2 years. After retreatment, only about a third recovered the level of clinical response they had achieved at the time of withdrawal. However, firm conclusions regarding the effects of withdrawal and retreatment could not be drawn due to the low numbers of patients in the study.

The proposed study is a followup of this small pilot study that will further our understanding of the benefits and risks of ETN withdrawal in patients who have achieved a significant clinical response. Much is known already from B1801031 about relapse rates of those achieving remission and continuing on ETN, therefore an open-label study estimating the relapse rates in such patients withdrawn from ETN is planned.

Overall, the benefits of ETN administration in patients with nr-ax SpA are expected to include reduced disease activity, including less pain, reduced inflammation of the SIJ, and improved physical function. Based on the safety experience from the B1801031 study combined with the long-term safety data and post-marketing safety experience in AS, an acceptable safety profile is expected in nr-ax SpA patients treated with ETN. Consequently, the risk-benefit balance of ETN for the treatment of nr-ax SpA is considered to be positive in patients who have high disease activity despite treatment with NSAIDs. Furthermore, the risk benefit may be more favorable in patients with objective evidence of inflammation, ie, those who have high CRP and/or MRI inflammation. The proposed study will further our understanding of the benefits and risks of ETN withdrawal in patients who have achieved a significant clinical response.

The dosing regimen chosen for this study is in agreement with the recommended dosage for AS in adults ages 18 or older.

Complete information for this compound may be found in the single reference safety document (SRSD), which for this study is the Investigator Brochure (IB).

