\*\*Subjects in this study cannot meet the criteria based on the second bullet (since defined radiographic sacroiliitis is an exclusion criterion). In order to meet the imaging criteria for ASAS, subjects must have positive sacroiliitis on MRI based on readings performed by the central imaging vendor. This criterion **cannot** be based on local MRI evaluation or historical MRIs.

If a subject has negative sacroiliitis on MRI, then they must have positive HLA-B27 plus 2 SpA features. Conversely, if a subject is HLA-B27 negative, then they must have positive sacroiliitis on MRI and at least 1 SpA feature. (See flowchart in [Appendix 6](#)).

The SpA features are listed below and defined in [Appendix 4](#).

- Inflammatory back pain;
  - Arthritis;
  - Enthesitis (heel);
  - Uveitis;
  - Dactylitis;
  - Psoriasis;
  - Crohn's/ Colitis;
  - Good response to NSAIDs;
  - Family history of SpA;
  - HLA-B27;
  - Elevated hsCRP.
6. Subjects must have positive MRI findings (active inflammation on MRI highly suggestive of sacroiliitis associated with SpA) and/or positive hsCRP (defined as hsCRP >3 mg/l).
  7. Active symptoms defined by an ASDAS CRP greater than or equal to 2.1 at the screening visit.
  8. Back pain with a less than favorable response to current intake of an NSAID at the optimal tolerated dose as determined by the investigator. Subjects must have experienced less than favorable response to at least 2 NSAIDs (including the current one) taken separately at the optimal tolerated dose with a total combined duration of >4 weeks.
  9. Subject must be taking a stable dose of an NSAID for at least 14 days before the first dose.
  10. Female or male 18 years or older (20 or older if required by local regulations) but less than 50 at the time of consent.

11. In the opinion of the investigator, subject is reasonable candidate for treatment with ETN.
12. No contraindication to MRI examination (metal implants or inability to lie flat for 30-60 minutes for example).
13. Negative serum pregnancy test performed at screening, negative urine pregnancy test performed prior to the first dose and negative serum pregnancy test collected for analysis prior to the first dose.
14. Ability to self-inject investigational product or have a designee who can do so.
15. Ability to store injectable investigational product under refrigerated conditions.
16. Demonstrated an adequate screening for tuberculosis (TB) in accordance with local country guidelines.

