#### **4.2. Inclusion Criteria – Period 2**

1. Completion of Period 1.
2. Subjects must achieve ASDAS CRP (inactive disease) less than 1.3 at the Week 24 visit in order to be eligible to enter Period 2.

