### **9.2.2. Analysis of Secondary Endpoints**

For the key secondary endpoint of time to flare, descriptive statistics will include median time to flare and 95% confidence interval using the Kaplan-Meier approach. In addition an estimate of the relative flare rates in the current study and that seen in those subjects in protocol B1801031 who met the treatment withdrawal criteria for the current protocol will also be obtained; subjects in B1801031 did not discontinue treatment and will serve as a reference population. For this estimate a Cox Proportional Hazards model will be used. A 99% confidence interval will be calculated for the Hazard Ratio. Additional sensitivity analyses evaluating the impact of covariates may be performed, details will be provided in the statistical analysis plan.

The efficacy upon retreatment will be assessed descriptively as the proportion of subjects who achieve an ASDAS CRP inactive disease less than 1.3; this will be expressed as a percent with 95% confidence interval.

Dichotomous clinical and subject rated endpoints measured during Periods 1 and 2 will be summarized as number evaluated, percent with response of interest and 95% confidence intervals.

For continuous clinical and subject rated endpoints measured during Periods 1 and 2, both raw and change values will be summarized with the following descriptive statistics: n, mean, standard deviation, min and max, median and the 25th and 75th percentiles (quartiles).

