## Appendix 6. ASAS Eligibility Flowchart

# ASAS Eligibility Flowchart

- Duration of symptoms >3months and < 5 years at time of consent.
- Diagnosis of axial spondyloarthritis, as defined by ASAS criteria.
- In order to meet imaging criteria for ASAS, subjects must have positive Sacroiliitis on MRI based on readings performed at BioClinica. Subjects negative for Sacroiliitis on MRI must have positive HLA-B27 plus 2 SpA features (one SpA feature must be elevated hsCRP). Conversely, subjects that are HLA-B27 negative must have positive Sacroiliitis on MRI plus 1 SpA feature.

Please note this is a portion of the overall eligibility criteria and these criteria alone do not make the subjects eligible for randomization! Subjects must meet eligibility requirements for radiological sacroiliitis. They are not eligible if the centrally read x-ray of the SI joint meets modified NY criteria.

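### The B1801031 reference group is chosen only by the withdrawal-entry rule, so any wider enrolment in that study would mix a population difference into the unadjusted time-to-flare comparison

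*SAP*

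**What the plan says.** **Reference filter.** SAP 5.2.4 includes B1801031 subjects "who met the entry requirements for the current trial withdrawal period". Protocol 9.2.2 describes those "who met the treatment withdrawal criteria for the current protocol will also be obtained".

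**What that filter contains.** Protocol 4.2 has two items: "Completion of Period 1", and "Subjects must achieve ASDAS CRP (inactive disease) less than 1.3 at the Week 24 visit".

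**What it leaves out.** Under Protocol 4.1, every B1801381 subject also had to meet the Period 1 criteria. Criterion 6 reads "Subjects must have positive MRI findings" (active sacroiliitis) "and/or positive hsCRP (defined as hsCRP >3 mg/l". Others are screening ASDAS CRP of at least 2.1 (criterion 7), symptoms for at least 3 months and under 5 years (criterion 4; Appendix 6 has "Duration of symptoms >3months and < 5 years at time of consent"), age 18 to under 50 (criterion 10), and inadequate response to at least two NSAIDs (criterion 8).

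**What is known of B1801031.** Protocol 1.2 describes a 12-week etanercept versus placebo comparison in nr-ax SpA with an open-label extension. Its eligibility criteria are not given.

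**Planned analyses.** SAP 5.2.4 plans Kaplan-Meier plots for both studies and a life-table sensitivity analysis. SAP 6.1.1.1 lists four Cox models: study alone; plus baseline variables (age, sex, region, CRP, MRI status, disease duration, NSAID response); plus ASDAS at Weeks 12 and 24; or plus sustained remission. Binary covariates that are rare in either study are left out. SAP 6.4 adds Cox models with study, one subgroup factor and their interaction, including MRI and CRP status.

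**The concern.** Comparing time to flare with continuing B1801031 subjects is a stated secondary objective (Protocol 2.1.2). Protocol 1.2 uses what is known from B1801031 to justify an open-label withdrawal study, so this reference group stands in for a control arm. The hazard ratio can be read as the effect of withdrawal only if the two groups come from comparable populations.

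A shared remission threshold at one time point does not ensure that. If B1801031 admitted people with no objective inflammation, longer disease, older age or lower entry activity, some of them could reach ASDAS CRP below 1.3 and enter the reference group, although nobody like them could enter B1801381. Any difference in their tendency to flare would then be credited to continuing treatment. The Kaplan-Meier plots, the life table and model 1 offer no protection, and no Cox model is named as the main one.

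**Working it through.** **1. The plan's own figures.** Protocol 9.1 gives half-widths only for single-arm proportions, checked with 1.96 × √(p(1−p)/n):
- Flare, p = 0.70, n = 96: 9.2% (stated as about 10%).
- Retreatment response, p = 0.60, n = 0.70 × 96 ≈ 67: 11.7% (stated as about 12%).

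Both agree, and neither depends on B1801031. No event count or target hazard ratio is stated for the cross-study comparison.

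**2. Period 1 criteria against the planned protection.**

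| Protocol 4.1 criterion | In reference filter? | Covariate in models 2–4? |
|---|---|---|
| MRI-positive and/or hsCRP >3 mg/L | No | MRI and CRP status |
| Screening ASDAS CRP ≥2.1 | No | No (model 3 uses Weeks 12 and 24 only) |
| Symptoms ≥3 months, <5 years | No | Disease duration |
| Age 18 to <50 | No | Age |
| Inadequate response to ≥2 NSAIDs | No | NSAID response, good or not |

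**3. Unadjusted comparison.** Let f be the ineligible share of the reference group and k their flare hazard relative to eligible reference subjects. Both are assumptions. The reference hazard is multiplied by 1 − f + f·k:

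| f | k = 0.5 | k = 2 |
|---|---|---|
| 10% | 0.95 | 1.10 |
| 20% | 0.90 | 1.20 |
| 30% | 0.85 | 1.30 |
| 40% | 0.80 | 1.40 |

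To put this on the hazard-ratio scale (continuing to withdrawn, as in SAP 5.2.4), take exponential times. The protocol's 70% flare at 40 weeks gives −ln(0.30)/40 = 0.0301 per week. Assuming 20% of eligible continuing subjects flare, the eligible-only ratio is ln(0.80)/ln(0.30) = 0.185. At f = 40% this becomes 0.148 (k = 0.5) or 0.259 (k = 2). Assumed continuing flare of 10% or 30% gives 0.088 or 0.296, with the same relative shifts.

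**4. Does adjustment remove it?** This was simulated with 20,000 subjects per study, censoring at 40 weeks and a true ratio of 0.185. Withdrawn subjects were 40% positive on both markers, 30% on MRI only and 30% on CRP only. The reference group had the same split plus a share f negative on both.

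| Assumed marker effects on hazard | f | Study only | Adjusted for MRI, CRP | Restricted, study only | Restricted, adjusted |
|---|---|---|---|---|---|
| Additive (log scale), 1.5 per positive marker | 20% | 0.168 | 0.183 | 0.190 | 0.187 |
| same | 40% | 0.157 | 0.190 | 0.196 | 0.193 |
| 1.2 per positive marker, extra 0.5 if both negative | 20% | 0.165 | 0.175 | 0.189 | 0.188 |
| same | 40% | 0.136 | 0.156 | 0.178 | 0.177 |
| No marker effect, extra 2 if both negative | 20% | 0.222 | 0.213 | 0.188 | 0.188 |
| same | 40% | 0.258 | 0.231 | 0.187 | 0.187 |

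With additive effects, adjustment essentially recovers 0.185. With an extra effect confined to the double-negative cell and f = 40%, the adjusted ratio is 0.156/0.185 = 0.84 or 0.231/0.185 = 1.25 times the truth. Restricted estimates stay within 0.177–0.196. At f = 40% the restricted reference has about 2,400 flares against about 14,000 in the withdrawn group, a simulation standard error of √(1/2,400 + 1/14,000) = 0.022 on the log scale, so small departures from 0.185 should not be read closely.

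**The case against.** The best defence has four parts.

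- **The harm depends on an unseen study.** A reader might infer that ineligible subjects are in the reference group and that the hazard ratio is biased. The documents do not support that: B1801031's eligibility is not given, so existence, share and direction are all unknown. This stands, and limits the point to a conditional one.
- **Period 1 completion might import Period 1 eligibility.** That reading is possible, but neither document says so or defines completion for a study without that period. The wording needs repair on either reading.
- **Much adjustment is already planned.** Three of four Cox models adjust for age, CRP, MRI, disease duration and NSAID response, and under additive effects that is nearly enough. The MRI subgroup model in SAP 6.4 also allows a contrast among MRI-positive subjects, all of whom satisfy criterion 6. This stands in large part. However, baseline ASDAS is not a covariate, sparse binary covariates can be dropped, each SAP 6.4 model handles one factor at a time, and no analysis restricts on all the criteria together.
- **The double-negative cell may not be empty in B1801381.** A reader might infer that it must be. SAP 6.1.1.1 gives no cut-off for normal versus high CRP, Appendix 4 of the protocol uses the upper normal limit rather than 3 mg/L, and SAP 3.4 takes the last screening or baseline value. Such subjects should be few or absent; emptiness is not established.

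The remark in Protocol 1.2 that "the risk benefit may be more favorable in patients with objective evidence of inflammation" concerns treatment benefit and risk. It is not evidence on flare hazard among continuing subjects in remission.

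**Conclusion.** The point holds in conditional form and is of moderate importance. The plan selects the reference group on remission alone and never aligns it with B1801381 eligibility. If B1801031 enrolled more widely, the Kaplan-Meier plots, life table and model 1 are exposed: a factor of 0.80 to 1.40 on the reference hazard for f of 10–40% and k of 0.5 to 2, all assumed. Models 2–4 would remove most of this if effects are additive; a residual of about 16% low to 25% high needed both a 40% ineligible share and an assumed double-negative effect. If no reference subject is ineligible, nothing changes.

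The illustration does not suggest that the contrast would disappear: with 20% continuing flare, the unadjusted ratio over the assumed range stays between 0.148 and 0.259. What is at risk is the size of the estimate on a secondary objective. The single-arm primary flare proportion is unaffected.

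**What to change.** In SAP 5.2.4 and 6.1.1.1:

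- Add Kaplan-Meier estimates and Cox models 1–4 restricted to B1801031 subjects who, at their own baseline, meet the checkable B1801381 Period 1 criteria: MRI-positive and/or hsCRP >3 mg/L, ASDAS CRP ≥2.1, symptom duration ≥3 months and <5 years, age 18 to <50, and inadequate response to at least two NSAIDs where recorded.
- Define what completing Period 1 means for a B1801031 subject.
- Report how many reference subjects are excluded.
- Present the restricted results beside those for the wider set.

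The cost is SAP wording and a data filter, with a smaller reference group and a wider interval in the restricted analysis. If nobody is excluded, comparability on these criteria is documented and the estimates do not change.
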